
Dosage/ Dosage Form, Route, And Dose Regimen
	
Phase I: Carfilzomib will be administered at 56 mg/m² Days 1, 2, 8, 9, 15, 16 of a 28-day cycle. Dexamethasone will be administered at 40 mg Days 1, 8 and 15 of every cycle. Ruxolitinib to determine maximum tolerated dose (MTD) will be administered orally at 5, 10 or 15 mg twice daily on Days 1-28. Cycles last for 28 days.
 
Phase II/Run-in Period: Carfilzomib at a twice weekly dose of 56mg/m² and dexamethasone will be administered following the Phase I schedule for all subjects who had received a carfilzomib dose less than the twice weekly dose of 56mg/m² prior to study enrollment to assess non-response.
 
Note: Subjects who previously received carfilzomib regimen with $\geq 56\text{mg/m}^2$ will proceed directly to Phase II/Ruxolitinib.
 
Non-responders (after Cycle 1): proceed to Phase II/Ruxolitinib.
 
Responders (after Cycle 1): carfilzomib-dexamethasone will be administered until disease relapse/ progression, at which time they will cross over to carfilzomib-dexamethasone-ruxolitinib (Phase II/Ruxolitinib) until disease relapse/progression.
 
Phase II/Ruxolitinib: Ruxolitinib will be administered orally at MTD on Days 1-28 for non-responders until disease relapse/progression. Cycles last for 28 days.

Statistical Analysis
	
Kaplan-Meier techniques will be used to estimate overall survival, progression-free survival, time to progression, time to best response, and duration of response. The 4-month PFS rate will be estimated based on the KM analysis with Greenwood’s Formula for the 95% confidence interval. The 4-month response rate will be estimated using all enrolled patients as the denominator with the associated 95% confidence interval by the Clopper-Pearson method. Safety and toxicity will also be assessed using frequencies and proportions. Logistic regression and Cox proportional hazards models will be used to assess the correlation between biomarkers and efficacy and toxicity outcomes.

SCHEMA

*MTD= Maximum tolerated Dose (Determined in Phase I)

LIST OF ABBREVIATIONS

Abbreviation	Spelled out abbreviation
ADL	Activities of daily living
ADRs	Adverse drug reaction
AE	Adverse event
ALL	Acute lymphoblastic leukemia
ANC	Absolute neutrophil count
AUC	Area under the curve
BID	Twice a day
BM	Bone marrow
BSA	Body surface area
BNP	Brain Natriuretic Peptide
BTZ	Bortezomib
BUN	Blood urea nitrogen
CFR	Code of Federal Regulations

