3 SUBJECT SELECTION

3.1 Accrual

This trial will enroll subjects with a diagnosis of relapsed or relapsed-refractory MM. Up to 18 DLT evaluable subjects will be enrolled in Phase I with 3 dose levels of ruxolitinib to be tested. Up to an additional 30 PFS4 evaluable subjects may be enrolled in the Phase II part at the MTD determined in Phase I.

All races and ethnic groups are eligible for this study.

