4.2.1 Phase I Design

Phase I will follow the standard 3 + 3 design with 3 to 6 subjects, depending on dose limiting toxicity (DLT) observed, at each dose level to be tested. Up to 3 dose levels will be tested. The overall duration of the Phase I portion of the study is expected to be no longer than 12 months.

Subjects will receive carfilzomib 56 mg/m²/day* IV over 30 minutes on Days 1, 2, 8, 9, 15 and 16 of a 28 day cycle. *Note: Subjects who have received CFZ < 56mg/m² more than 60 days prior to informed consent should receive CFZ 20mg/m² on Days 1 and 2 of the first cycle of protocol therapy with subsequent doses of 56mg/m².

Dexamethasone is administered orally prior to carfilzomib at 40 mg on Days 1, 8, and 15 of a 28 day cycle. Note: a 20 mg dose may be considered for subjects ≥ 75 years of age and for diabetic subjects.

Ruxolitinib is administered orally with or without food twice daily for 28 days of a 28 day cycle

Table 1: Dose Levels to be Tested

Cohort	Carfilzomib	Dexamethasone	Ruxolitinib
Each cycle is 28 days	IV over 30 min	PO	PO

	Days 1, 2, 8, 9, 15, 16	Days 1, 8 and 15	Twice Daily Days 1-28
Cohort 1	56 mg/m ^{2a}	40 mg PO ^b	5 mg
Cohort 2	56 mg/m ^{2a}	40 mg PO ^b	10 mg
Cohort 3	56 mg/m ^{2a}	40 mg PO ^b	15 mg

- a. Subjects who have received CFZ < 56mg/m² more than 60 days prior to informed consent should receive CFZ 20mg/m² on Days 1 and 2 of the first cycle with subsequent doses of 56mg/m². See section 4.2.1.1 for MTD guidance
- b. A 20 mg dose may be considered for subjects ≥ 75 years of age and for diabetic subjects.

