4.2.2 Phase II Design

Subjects in the Phase II/Run-in period will receive an initial cycle with carfilzomib at the twice weekly dose of 56mg/m² and dexamethasone. Following Cycle 1, a response assessment will be done. Subjects with a response of PR or better (“Responders”) will continue therapy with carfilzomib and dexamethasone. After these responding subjects subsequently progress, they will be treated with ruxolitinib (at the dose established in Phase 1) in combination with carfilzomib and dexamethasone. Subjects with a response of less than PR (“Non-responders”) will add ruxolitinib at the dose established in Phase I to carfilzomib and dexamethasone for all subsequent cycles. The cycle when ruxolitinib is added will be considered Cycle 1 (cycle numbers will start over). Disease evaluation assessment results should be available prior to dosing on Day 1 of each cycle of Phase II until initiation of ruxolitinib treatment (to ensure initiation of ruxolitinib occurs on Day 1 of a cycle).

Enrollment in the Phase II part of the study will be carried out in two stages. During the first stage, 10 PFS evaluable subjects (Section 13.3) will be enrolled. Enrollment and Stage 1 analysis of the first ten subjects on the three drugs (carfilzomib-ruxolitinib-dexamethasone) will be completed to determine if at least 3 of 10 subjects are alive and progression free at 4 months. If so, an additional 20 subjects will be enrolled (a total of 30 subjects) during the second stage. If at least 11 of 30 subjects are alive and progression free at 4 months, the null hypothesis will be rejected (based on binomial probabilities, see Section 13.1.2). The overall duration of the Phase II portion of the study is expected to be no longer than 24 months. For both Phase I and Phase II, subjects will be assessed for response after each cycle with confirmation of response according to IMWG response criteria regardless of dose level treated. Doses of each study drug may be interrupted or reduced in an attempt to manage toxicity.

Table 2: Phase II/Run-In Dosing^a

Drug	Dose	Route	Schedule	Cycle Length
------	------	-------	----------	--------------

Dexamethasone	40 mg ^b	PO	D1, 8, and 15 (Prior to carfilzomib)	28 days
Carfilzomib	56 mg/m ^{2c}	Intravenously (IV) over 30 minutes	D1, 2, 8, 9, 15, and 16	

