13.3 Analysis Populations

For the Phase I part of the study, the dose escalation and MTD evaluation will be conducted on the population who initiate Cycle 1, Day 1 treatment, and who meet the DLT evaluable criteria as described in Section 4.3. For the Phase II part of the study, the PFS4 evaluable population will include all subjects who initiate treatment with ruxolitinib, have experienced a PFS event within 4 months from the start of ruxolitinib treatment, or have at least 4 months of follow up time from the start of ruxolitinib treatment. The primary efficacy analysis will be conducted on the PFS4 evaluable population. Response-evaluable population will include all subjects (both Phase I and Phase II) who have baseline evaluation, measurable disease, and initiate study

treatment followed by at least one efficacy measurement. All response endpoints will be conducted on the response-evaluable population.

All other efficacy and ruxolitinib safety analyses will be conducted on the population of subjects (both Phase I and Phase II) who initiate treatment with ruxolitinib. Additionally, an analysis will be conducted on safety data collected from Cycle 1 through the cycle prior to initiation of ruxolitinib treatment (for all Phase II subjects initiating Cycle 1 with carfilzomib plus dexamethasone).

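### Secondary efficacy, response and ruxolitinib safety pool every Phase I dose level with Phase II, with no breakdown by dose, phase or run-in status

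*Combined protocol and SAP*

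**What the plan says.** Section 13.3 sets the population for non-primary efficacy and ruxolitinib safety: "All other efficacy and ruxolitinib safety analyses will be conducted on the population of subjects (both Phase I and Phase II") who begin ruxolitinib. Response endpoints have their own population, also drawn from both parts: "Response-evaluable population will include all subjects (both Phase I and Phase II) who have baseline evaluation, measurable disease", with treatment started and at least one efficacy measurement.

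The two parts differ in dose and in the route to ruxolitinib.

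- **Phase I dose.** Section 3.1: "Up to 18 DLT evaluable subjects will be enrolled in Phase I with 3 dose levels of ruxolitinib to be tested". In the Protocol Summary, ruxolitinib in Phase I "will be administered orally at 5, 10 or 15 mg twice daily on Days 1-28". Section 4.2.1: "Phase I will follow the standard 3 + 3 design with 3 to 6 subjects, depending on dose limiting toxicity (DLT) observed".
- **Phase II dose.** Section 3.1: "Up to an additional 30 PFS4 evaluable subjects may be enrolled in the Phase II part at the MTD determined in Phase I".
- **Route to ruxolitinib.** Section 4.2.2: "Subjects in the Phase II/Run-in period will receive an initial cycle with carfilzomib" and dexamethasone. Ruxolitinib is added after less than PR at the end of that cycle, or after later progression in those who responded. Subjects whose prior carfilzomib was at least 56 mg/m² bypass this step (Tables 2 and 3). Phase I has no run-in; all three drugs start together.

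Section 13.4.2.2 gives Kaplan-Meier summaries and proportions with Clopper-Pearson intervals, and Section 13.4.3 gives adverse event frequencies and dose intensity. Neither mentions presentation by dose level, phase or run-in status.

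**The concern.** Two kinds of mixing follow if the plan is carried out as written.

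The first is dose. Adverse event rates, dose intensity, PFS, OS and response combine subjects on 5, 10 and 15 mg twice daily with subjects at the MTD. A reader of the final report wants the toxicity and activity of the dose carried forward, and the pooled figure is a weighted average over doses.

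The second is the carfilzomib increase. Section 3.1.1 accepts prior carfilzomib at 20/27 mg/m². In Phase II such a subject first shows whether 56 mg/m² with dexamethasone is enough; in Phase I the same subject receives the higher carfilzomib dose and ruxolitinib at once. PFS, OS and response are counted from ruxolitinib start (Sections 13.2.3 to 13.2.5). Benefit due to carfilzomib alone is therefore credited to the triplet in Phase I, whereas the run-in is there to screen it out. Section 13.1.2 describes the question as the effect of adding ruxolitinib, so this matters for how the secondary results are read.

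**Working it through.** **The plan's own figure.** The only powered analysis is the Phase II two-stage design (Section 13.1.2): continue with at least 3 of 10, reject with at least 11 of 30, 25% against 50%. With X1 ~ Bin(10, p), the rejection probability is the sum over x1 = 3 to 10 of P(X1 = x1) × P(Bin(20, p) ≥ 11 − x1).

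- At p = 0.25: 0.0914, within the stated 0.10.
- At p = 0.50: 0.9116, meeting the stated 90%.
- Probability of stopping after stage 1: 0.526 at 25% and 0.055 at 50%.

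The design reproduces. The stopping probability matters here because it determines how often the pool would consist largely of Phase I subjects.

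**Composition of the pool.** Inputs are the escalation rules of Section 4.2.1.1 and the Phase II sizes of 10 or 30. I assume that each cohort below the MTD has 3 or 6 subjects; that an MTD of 5 or 10 mg has 6 subjects at the MTD and one exceeded cohort of 3 or 6 above it; and that an MTD of 15 mg has 3 or 6 subjects at that level. Only DLT-evaluable Phase I subjects are counted. Share off the MTD = (below + above) / total.

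| MTD (twice daily) | Off-MTD subjects | Phase II n | Pool | Off-MTD share | Phase I share |
|---|---|---|---|---|---|
| 5 mg | 3 or 6, all above | 30 | 39–42 | 7.7–14.3% | 23.1–28.6% |
| 10 mg | 6 to 12, below and above | 30 | 42–48 | 14.3–25.0% | 28.6–37.5% |
| 15 mg | 6 to 12, all below | 30 | 39–48 | 14.3–26.7% | 23.1–37.5% |
| 5 mg | 3 or 6, all above | 10 | 19–22 | 15.8–27.3% | 47.4–54.5% |
| 10 mg | 6 to 12, below and above | 10 | 22–28 | 27.3–42.9% | 54.5–64.3% |
| 15 mg | 6 to 12, all below | 10 | 19–28 | 27.3–48.0% | 47.4–64.3% |

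Examples: 3/39 = 7.7%; 12/48 = 25.0%; 12/45 = 26.7%; 12/25 = 48.0%.

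**Effect on an estimate.** Pooled rate − MTD rate = f × (off-MTD rate − MTD rate), where f is the off-MTD share. The documents give no rates by dose, so the difference is an assumption.

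- A 20-point difference: 0.077 × 20 = 1.5 to 0.267 × 20 = 5.3 points if Phase II completes; 0.158 × 20 = 3.2 to 0.48 × 20 = 9.6 points if it stops at stage 1.
- A 50% rate at the MTD and 25% off it, 12 of 48 off: (12 × 0.25 + 36 × 0.50)/48 = 43.8%.
- Section 13.4.3 puts the Grade 3/4/5 AESI composite at about 0.30 on carfilzomib-dexamethasone. With 30% below the MTD and an assumed 40% at it: (12 × 0.30 + 36 × 0.40)/48 = 37.5%, a shift of 2.5 points.

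The sign depends on whether the off-MTD subjects lie below or above the MTD.

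**Carfilzomib increase.** No number can be given. The share of Phase I subjects with prior carfilzomib below 56 mg/m², and their response to the increase alone, are not in the documents.

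**Precision given up.** 95% Clopper-Pearson intervals at an observed 50%:

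| Set | n | Interval | Half-width |
|---|---|---|---|
| Full pool | 48 | 35.2–64.8% | 14.8 |
| MTD-treated | 36 | 32.9–67.1% | 17.1 |
| Phase II only | 30 | 31.3–68.7% | 18.7 |

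If Phase II stops at 10, the normal approximation for Phase II alone gives 1.96 × √(0.25/10) = 31 points. For 13 to 16 MTD-treated subjects it gives 1.96 × √(0.25/13) = 27 and 1.96 × √(0.25/16) = 24.5.

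**The case against.** The strongest reply is that no decision rests on the pooled set. The primary PFS4 test is a Phase II analysis, the AESI stopping rule counts Phase II subjects on ruxolitinib, and DLT and MTD are judged by cohort. The pooled analyses are descriptive, with no test and no power claim. All of this stands, and it limits the weight of the point.

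The plan can also say that Section 1.2 sets secondary efficacy in subjects who receive the triple combination, which Section 13.3 implements, and that Section 13.3 says who is included without forbidding tables by dose. That is a fair reason to keep the pooled set. It does not supply the missing breakdown. Section 1.2 names safety for Phase I and Phase II separately, yet Section 13.3 does not carry that split into the ruxolitinib analyses.

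On the run-in, Phase II is itself mixed: non-responders, responders who later progress, and direct entrants. Phase I subjects with prior carfilzomib of at least 56 mg/m² resemble the direct entrants. So the problem is confined to Phase I subjects with lower prior doses, and Phase II alone would not be homogeneous either. This is why results by run-in status are needed.

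A reader might infer more than the documents support:

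- **That the pooled estimate describes no regimen.** Planned carfilzomib and dexamethasone are common to all cohorts, and about 73 to 92% of a completed pool is at the MTD.
- **That a quarter of subjects are below the MTD.** Twelve of 48 below it requires an MTD of 15 mg, both lower cohorts expanded to six, and six at the top level.
- **That toxicity at the MTD is understated.** With an MTD of 5 mg, every off-MTD subject is above it and the bias could run the other way.

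**Conclusion.** The point holds as a deficiency in how secondary and safety results are defined and reported. It is not a threat to the primary conclusion. Section 13.3 pools both phases for secondary efficacy, response and ruxolitinib safety, and nothing in Section 13.4 separates them.

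If Phase II completes, about 8 to 27% of the pool is off the MTD, and plausible shifts are a few percentage points, smaller than the interval half-widths. If Phase II stops at stage 1, which has probability 0.526 under the null, Phase I makes up about half or more of the pool and the off-MTD share can reach 48%. The pooled figures then represent the MTD regimen least well.

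The carfilzomib contribution in Phase I could raise pooled response and PFS, by an amount the documents do not allow one to estimate. The shares rest on the 3 + 3 rules and DLT-evaluable counts; the shifts rest on assumed rate differences.

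**What to change.** Amend Sections 13.3 and 13.4 as follows.

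- **Safety.** Make all subjects treated at the MTD (Phase II plus the Phase I MTD cohort) the main set for ruxolitinib safety and dose intensity.
- **Secondary efficacy and response.** Report MTD-treated subjects, with Phase II shown separately and by run-in status: non-responder, responder who later progressed, or direct entry. Showing Phase II separately is needed because the Phase I MTD cohort still carries the carfilzomib-increase problem.
- **Phase I.** Tabulate safety and efficacy by dose level.
- **Pooled set.** Keep it, labelled as supportive.

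Making Phase II alone the main efficacy set is more debatable, since it discards Phase I subjects treated at the same ruxolitinib dose; the layout above does not require it.

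The data are already collected, and neither conduct nor sample size changes. The cost is a few more tables and wider intervals: about 2 points of half-width for 36 MTD-treated subjects and 4 for Phase II alone, compared with 48 pooled. If Phase II stops at 10 the loss is larger, with about ±31 points for Phase II alone. The run-in subgroups will be small and should be described without formal comparison.

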13.4 Analysis Methods

13.4.1 Timing of Analyses

For the Phase I part of the study, an evaluation of the data will take place after each subject completes Cycle 1. For the Phase II part of the study, AESIs will be continuously evaluated in order to assess the Bayesian stopping rules for toxicity described in Section 13.4.3. Additionally, the stage 1 analysis will occur after the first 10 PFS evaluable subjects enrolled have progressive disease, have died, or have at least 4 months of follow up time from ruxolitinib treatment start. The stage 2 analysis will occur after 30 PFS evaluable subjects have progressive disease, have died, or have at least 4 months of follow up time. For both Phase I and Phase II, a follow up analysis will occur when all enrolled subjects have progressed, have died, have become lost to follow up or withdrawn from the study, or have at least two years of follow up time after initiation of treatment with ruxolitinib. A final analysis (for both Phase I and Phase II) will occur when all subjects have died, have become lost to follow up or withdrawn from the study, or have at least 3 years of follow up time after initiation of treatment with ruxolitinib.

13.4.2 Efficacy Analyses

13.4.2.1 Primary Analysis (Phase II)

The frequency and proportion of subjects who are alive and progression free at 4 months will be calculated with a corresponding 95% confidence interval using the Clopper-Pearson method. A one-sided test for binomial proportions using the rejection regions described in Section [13.1.2](#) will be carried out, testing the null hypothesis that the PFS4 rate is less than or equal to 25%.

13.4.2.2 Secondary Analyses

OS, PFS, time to progression, duration of response, and time to best response will be analyzed using Kaplan Meier techniques. Medians, 25th, and 75th percentiles will be estimated. Selected landmark rates will be estimated using the product limit function. Objective response rate, disease control rate, and clinical benefit rate will be analyzed using frequencies and proportions. Ninety-five percent confidence intervals will be estimated using the Clopper-Pearson method.

13.4.3 Safety Analyses

Treatment administration will be summarized descriptively in terms of cumulative dose administration and dose intensity of ruxolitinib (adjusting for dose delays and reductions). Additionally, the relative dose intensity will be calculated in terms of the actual dose intensity as percent of the intended dose intensity. The maximum grade for each type of adverse event will be recorded for each subject and treatment-emergent adverse events (TEAEs) will be identified. TEAEs are defined as follows:

- An adverse event that occurs after treatment start that was not present at the time of treatment start; or
- An adverse event that increases in severity after treatment start if the event was present at the time of treatment start.

TEAEs will be summarized using frequencies and proportions, and these will be reviewed to determine patterns. Additionally, the relationship of the adverse event(s) to the study treatment will be taken into consideration.

Clinical laboratory tests (hematology, chemistry, coagulation panel, BNP), vital signs, and ECHO/MUGA/cardiac MRI (ejection fraction (%)) will be summarized with descriptive statistics.

Phase II Stopping Rule

It is estimated that the composite rate of Grade 3/4/5 AESIs (as defined in Section 13.2.10) in relapsed or refractory multiple myeloma patients treated with carfilzomib plus dexamethasone is approximately 0.30³⁰. If it becomes evident that the Grade 3/4/5 AESI rate convincingly exceeds 0.30, the study will be halted. Enrollment will be suspended if the posterior probability of the Grade 3/4/5 AESI rate exceeding 0.30 is 0.75 or higher. The prior distribution for this monitoring rule is beta (3,7). This means that our prior assumption regarding the proportion of Grade 3/4/5 AESI's is 0.30, and there is 90% probability that this proportion is between 0.098 and 0.550. The operating characteristics of the stopping rule are given in the following table and are based on 5000 simulations.

Operating Characteristics of the Stopping Rule

Number of Subjects with an AESI	Number of Treated Subjects	Posterior Probability: Pr(AESI Rate>0.30 Data)
3	5	0.781
4	8	0.779
5	11	0.761
6	14	0.777

7	17	0.767
8	20	0.768
9	23	0.772
10	26	0.770
11	29	0.761

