1.2 Secondary Objectives

Secondary objectives include evaluation of objective response rate (ORR), clinical benefit rate, disease control rate, progression-free survival, time to best response, overall survival, time to progression and duration of response in subjects that receive treatment with the triple drug combination, and further evaluation of the safety and tolerability of the combination of carfilzomib, dexamethasone and ruxolitinib (Phase I) and carfilzomib, dexamethasone +/- ruxolitinib (Phase II).

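### Run-in and ruxolitinib-period adverse events are summarised only as crude proportions over periods of unequal length, so the two safety tables can mislead when read side by side

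*Combined protocol and SAP*

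**What the plan says.** Section 1.2 includes among the secondary objectives the safety and tolerability, in Phase II, of carfilzomib and dexamethasone with or without ruxolitinib. Section 13.3 serves this with two analyses. The first: "ruxolitinib safety analyses will be conducted on the population of subjects (both Phase I and Phase II) who initiate treatment with ruxolitinib". The second: "an analysis will be conducted on safety data collected from Cycle 1 through the cycle prior to initiation of ruxolitinib treatment". For TEAEs, section 13.4.3 gives one method: "TEAEs will be summarized using frequencies and proportions, and these will be reviewed to determine patterns". It adds that relationship to study treatment will be considered. Dose administration and dose intensity are summarised for ruxolitinib only (13.2.10, 13.4.3). No exposure summary is named for the run-in, and no person-time rate or common time window for either period.

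The two periods end by different rules. On the run-in, the Protocol Summary says "Non-responders (after Cycle 1): proceed to Phase II/Ruxolitinib" and "Responders (after Cycle 1): carfilzomib-dexamethasone will be administered until disease relapse/ progression". Subjects with prior carfilzomib at 56 mg/m² or more have no run-in (4.2.2, Tables 2 and 3). Ruxolitinib continues until progression or another reason listed in 5.5. Adverse events are recorded until 30 days after the last dose (9.4), and for anyone who crosses over that tail falls in the ruxolitinib period.

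**The concern.** The proportion of subjects with at least one event rises with time at risk. A non-responder is observed for one cycle in the first table and for the whole ruxolitinib course plus 30 days in the second. If most run-in subjects are non-responders, the ruxolitinib table will show higher percentages even if ruxolitinib adds no toxicity. The run-in is the only carfilzomib-dexamethasone safety experience inside this single-arm Phase II, so readers interested in the with-or-without-ruxolitinib objective will naturally put the two tables together. With no run-in exposure reported, they could not correct for the difference afterwards.

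**Working it through.** **Inputs**
- Run-in for a non-responder: one 28-day cycle, 28/30.4375 = 0.92 months (Protocol Summary, 4.2.2).
- Median PFS: 2 months (null) and 4 months (alternative), from 13.1.2. Used here for time on ruxolitinib, which is an assumption.
- Adverse-event tail: 30 days = 0.99 months (9.4).
- Run-in responders: response rate 23.7%, median PFS 3.7 months and duration of response 7.8 months, from the single-agent carfilzomib study quoted in 2.2.4. That study concerns a different population, so these serve only as a range.
- Event risk: not in the documents. Assumed 10% per 28-day cycle (range 5% to 30%), constant hazard, the same in both periods.

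**The plan's own figure.** Exponential PFS gives 0.5^(4/2) = 0.25 and 0.5^(4/4) = 0.50, matching the 25% and 50% in 13.1.2. The documents give no figure for event proportions by period.

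**Period lengths against a one-cycle run-in.** Medians: 2/0.92 = 2.2 and 4/0.92 = 4.3 times. Means (median/ln 2) are 2.89 and 5.77 months, or 3.1 and 6.3 times; with the tail, 4.2 and 7.3 times.

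**Crude proportions with no added toxicity.** Hazard λ = −ln(1 − p)/0.92. On ruxolitinib the proportion is λ/(λ + h), with h = ln 2/median. For p = 10%, λ = 0.1054/0.92 = 0.1145 per month:
- median 2 months: 0.1145/(0.1145 + 0.3466) = 0.248
- median 4 months: 0.1145/(0.1145 + 0.1733) = 0.398
- with the tail, 1 − [h/(h + λ)]·exp(−0.99λ): 0.329 and 0.462

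| Run-in, one cycle | Ruxolitinib, median 2 months | Ruxolitinib, median 4 months |
|---|---|---|
| 5% | 14% | 24% |
| 10% | 25% | 40% |
| 20% | 41% | 58% |
| 30% | 53% | 69% |

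**Adding run-in responders (10% per cycle).** A fraction f stays for a further exponential time with median m and exit hazard g = ln 2/m. The run-in proportion is (1 − f)p + f[1 − (1 − p)·g/(g + λ)], and the mean run-in is 0.92 + f·m/ln 2 months. The ruxolitinib proportion (without tail) stays at 25% to 40%.

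| f | m (months) | Run-in proportion | Mean run-in (months) | Mean length ratio, ruxolitinib to run-in |
|---|---|---|---|---|
| 0 | – | 10% | 0.92 | 3.1 to 6.3 |
| 10% | 3.7 / 7.8 | 13% / 15% | 1.45 / 2.05 | 2.0 to 4.0 / 1.4 to 2.8 |
| 23.7% | 3.7 / 7.8 | 18% / 22% | 2.19 / 3.59 | 1.3 to 2.6 / 0.8 to 1.6 |
| 40% | 3.7 / 7.8 | 24% / 30% | 3.06 / 5.42 | 0.9 to 1.9 / 0.5 to 1.1 |

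With 40% responders and m = 7.8, the run-in shows 30% against 25% on ruxolitinib at a 2-month median, so the direction reverses.

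**Front-loaded hazard, no responders.** If the hazard in the ruxolitinib period is half that of the run-in, 10% becomes 14% to 25%. If it is a quarter, 10% becomes 8% to 14%.

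**With person-time.** Under the equal constant hazard both periods give 0.1145 first events per person-month (× 0.92 = 0.105 per patient-cycle), ratio 1.0. Restricted to the first 28 days, both show 10%.

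**The case against.** The strongest reply is that the plan never compares the two periods. Section 1.2 asks for an evaluation, and 13.3 adds the run-in summary as a separate analysis with no difference or test. Excess toxicity is addressed elsewhere: the AESI stopping rule counts events related to the ruxolitinib-containing regimen against a fixed reference of 0.30, not against the run-in. A reader might infer that the plan itself attributes an excess to ruxolitinib; the text does not do so. This stands, and it limits the harm to how two descriptive tables may be read.

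A reader might also infer a bias of known direction, built in by design. That does not hold either. Only the non-responder run-in is fixed at one cycle, while responders remain in it until progression. Section 5.1.3 describes a first-dose effect in the first or second carfilzomib cycle, which suggests that some toxicity is front-loaded. Section 5.5 lists reasons besides progression for stopping, which shorten the ruxolitinib period. On the other side, 13.1.2 assumes a 2-month median PFS for carfilzomib-dexamethasone retreatment, so few or short-lived responders fits the protocol's own planning.

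Nor would person-time make the contrast unbiased. The run-in always comes first, and subjects reach ruxolitinib through non-response or progression. The ruxolitinib set pools Phase I subjects at several dose levels and Phase II subjects who skip the run-in, and some subjects have a lower carfilzomib dose on the first two days of run-in cycle 1. Precision is poor too: with 20 run-in subjects at one cycle each (assumption) and 2 events, the exact Poisson 95% interval is about 0.01 to 0.36 per cycle.

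**Conclusion.** The point holds as a reporting gap with a cheap remedy. The two safety analyses use crude proportions over periods whose lengths follow different rules, and the plan supplies no run-in exposure with which to interpret them. With few responders and an equal constant hazard, the ruxolitinib proportion would be about 2.5 to 4 times the run-in proportion at 10% per cycle with no added toxicity. That size rests on the assumed event risk, on time on ruxolitinib following PFS, and on the responder fraction. With 23.7% responders the gap is clearly smaller, and with many responders or a front-loaded hazard it can vanish or reverse. Because neither size nor direction can be fixed in advance, the crude proportions cannot separate a drug effect from a difference in observation time. The primary endpoint and the stopping rule are unaffected.

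**What to change.** In section 13.4.3, keep the crude tables and add:
- total person-time at risk for the run-in and for the ruxolitinib period;
- exposure-adjusted incidence by period (subjects with a first event per patient-cycle at risk, with 95% CI) for Grade 3 or higher TEAEs and for the composite AESI, not for each AESI term, given the small numbers;
- a first-28-day table of run-in cycle 1 against ruxolitinib cycle 1, in subjects who had both.

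State that the crude proportions of the two periods are not to be compared directly. State also that the added tables are descriptive and supportive, because treatment order, disease stage and population still differ. Conclusions on added toxicity should not be made to rest on them.

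The cost is a few sentences and two tables. Section 9.4 already has adverse events and treatment administration recorded in the eCRF, and the split in 13.3 already requires events to be assigned to a period. The downsides are wide intervals and a constant-hazard assumption, which the first-cycle table partly checks. No treatment, visit or sample size changes.
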